- i. Rapid serological test for anti-SARS-CoV-2 antibody will collect blood from a small puncture in the finger (finger-prick test at screening).
- j. If a rapid serologic test is completed ≤ 3 days before vaccination, a repeat test is not required on Day 1
- k. Investigator must check for clinically significant acute illness or body temperature $\geq 38.0^{\circ}\text{C}/100.4^{\circ}\text{F}$ at the time of vaccination. If any of these events occur at the scheduled time for vaccination, the vaccination can be rescheduled as long as this is in agreement with the allowed windows. If the vaccination visit cannot be rescheduled within the allowed window or the contraindications to vaccination persist, the sponsor should be contacted for further guidance. The investigator should also check if any other reasons, as listed in Section 7.1, have been met and would prevent further study vaccination.
- l. For participant of childbearing potential only.
- m. Whole blood samples will be used for complete blood cell count, including platelet count (hematology, see Section 10.2, Appendix 2), in a local laboratory or substitute for local laboratory, depending on local feasibility towards turnaround time of sample processing. Results should be available within 72 hours. The division of volumes between whole blood, plasma and serum is described in the laboratory manual. Serum and plasma are to be stored centrally for future testing to evaluate the impact of any potential thromboembolic events. Samples can also be tested (centrally) for anti-PF4 antibodies and platelet activation assay (if HIT/PF4 is positive). Unused samples may be used for immunogenicity testing.
- n. After each vaccination, participants will remain under observation at the study site for at least 30 minutes (or longer if required by institutional/local practice) for the presence of any acute reactions and solicited events. Any solicited local (at injection site) and systemic AEs, unsolicited AEs, SAEs, concomitant medications, and vital signs will be documented by study-site personnel following this observation period and participants will be allowed to leave the study site after it is documented that the required minimum post-vaccination observation period is complete.

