After each vaccination, participants will remain under observation at the study site for at least 30 minutes for the Dose Selection Cohort (or longer if required by institutional/local practice) and will be closely observed by study site staff. Necessary emergency equipment and medications must be available in the clinic to treat severe allergic reactions.

^aThis was expected as the pediatric studies were conducted in malaria-endemic regions. The imbalance in the frequency of malaria between Ad26 participants and placebo participants can largely be explained by the fact that the active control group (MenACWY) of study VAC52150EBL3001 was not included in the pooling.

Capillary Leak Syndrome

Capillary leak syndrome (CLS) is a rare disease that causes edema, hypoproteinemia, episodic hypotension, dyspnea, hyponatremia, and weight gain that can be life-threatening. Although the underlying pathology is currently unknown, CLS is thought to be secondary to disruption of the endothelium and generalized edema. No cases of CLS have been reported in Ad26.COV2.S vaccine studies. Individuals with a history of CLS will be excluded from participating in this study (Section 5.2; Exclusion Criterion 24) and CLS is a contraindication for administering a second dose of the study vaccine (Section 7.1).

Pregnancy and Birth Control

The effect of the study vaccine on a fetus or on a nursing baby is unknown.

Given the limited number of incident pregnancies in the clinical studies with Ad26-based vaccines in the AdVac® safety database report (HIV vaccine: 20 pregnancies in participants and 10 in partners of participants; Ebola vaccine: 32 pregnancies in participants and 13 in partners of participants), it is not possible at present to draw firm conclusions on the safety of the vaccines when administered around the time of conception or prior to the initiation of the pregnancies. There is currently no concerning pattern of AEs in the pregnancies initiated around the time of vaccination or after exposure to the Ad26-based vaccines in the Janssen vaccines clinical development programs.

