Participants of childbearing potential will be required to agree to practicing an acceptable effective method of contraception and agree to remain on such a method of contraception from providing consent or assent until 3 months after receiving study vaccine (see Section 5.1). Participants who are pregnant or breastfeeding will be excluded from the study. Participants who become pregnant during the study will not receive further study vaccine but should continue to undergo all procedures for surveillance and follow-up of COVID-19 and all safety follow-up as outlined in the protocol for all participants.

Risks from Blood Draws

Blood draws may cause pain, tenderness, bruising, bleeding, dizziness, vasovagal response, syncope, and rarely, infection at the site where the blood is taken.

Risks from Collection of Nasal Swab Samples

Collection of a nasal swab sample may cause a nosebleed.

Theoretical Risk of Enhanced Disease

VAERD has been described for SARS-CoV and MERS-CoV in some animal models (Agrawal 2016; Bolles 2011; Deming 2006; Honda-okubo 2015; Houser 2017), and is associated with non-neutralizing antibodies and a Th2-skewed immune response, but proof of human SARS-CoV or MERS-CoV VAERD does not exist as these candidate vaccines were never tested for efficacy nor used in outbreak situations. In contrast, the Ad26-based vaccines have been shown to induce a clear Th1-skewed immune response and generate potent neutralizing antibody

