- b. Other licensed (not live) vaccines within 14 days before or after planned administration of a study vaccination.

12 Participant received an investigational drug (including investigational drugs for prophylaxis of COVID-19) or used an invasive investigational medical device within 30 days or received investigational immunoglobulin or monoclonal antibodies within 3 months, or received convalescent serum for COVID-19 treatment within 4 months, or received an investigational vaccine (including investigational Adenoviral-vectorized vaccines) within 6 months before the planned administration of the first dose of study vaccine or is currently enrolled or plans to participate in another investigational study during the course of this study.

Note: Participation in an observational clinical study is allowed at the investigator's discretion; please notify the sponsor (or medical monitor) of this decision.

Efforts will be made to ensure inclusion of participants who have not been previously enrolled in coronavirus studies and to prevent participants from subsequently enrolling in other coronavirus studies during their participation in this study.

The use of any coronavirus vaccine (licensed or investigational) other than Ad26.COV2.S is disallowed at any time prior to vaccination (see also exclusion criterion 18) and during the study.

13 Participant is pregnant.

14 Participant has a contraindication to IM injections and blood draws eg, bleeding disorders.

15 Participant is a family member of the investigator or study site, with direct involvement in the proposed study or other studies under the direction of that investigator or study site, or a known family member of the sponsor.

16 Participant has chronic active hepatitis B or hepatitis C infection per medical history.

17 Participant or participant's parent(s)/legal guardian who, in the opinion of the investigator, is unlikely to adhere to the requirements of the study or participant who is unlikely to complete the full course of vaccination and observation.

18 Participant previously received a coronavirus vaccine.

19 History of confirmed SARS or MERS.

20 Criterion removed per Amendment 1

21 An adolescent of a parent/legal guardian not capable of understanding the key aspects of the study and their requirements for participation (only applicable if parent[s]/legal guardian must sign the ICF according to local regulations).

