22 Participant's parent(s)/legal guardian is <18 years of age and not of legal age according to local regulations.

23 Criterion added per Amendment 1

23.1 For Part 1 only: Participant has a positive diagnostic test result for past (serological testing) SARS-CoV-2 infection at screening.

24 Criterion added per Amendment 1

24.1 History of CLS.

25 Criterion added per Amendment 1

25.1 A participant that is on medication that may lead to risk of blood dyscrasias or thrombotic events.

26 Criterion added per Amendment 1

26.1 A participant has a history of any serious, chronic, or progressive neurological disorders or seizures including Guillain-Barré syndrome, with the exception of febrile seizures during childhood.

27 Criterion added per Amendment 2

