7. DISCONTINUATION OF STUDY VACCINATION AND PARTICIPANT DISCONTINUATION/WITHDRAWAL

7.1. Discontinuation of Study Vaccination

Study vaccinations will be withheld for the reasons listed below. These participants must not receive any further doses of study vaccine but should remain on study for follow-up of safety and immunogenicity as indicated in the Schedule of Activities (Section 1.3). Additional unscheduled visits may be performed for safety/reactogenicity reasons, if needed. In case of questions, the investigator is encouraged to contact the sponsor.

- Any related AE, worsening of health status or intercurrent illnesses that, in the opinion of the investigator, requires discontinuation from study vaccine
- The participant becomes pregnant
- Unblinding (other than scheduled unblinding) on the participant level that, in the opinion of the sponsor, would compromise the integrity of the data
- Anaphylactic reaction following vaccination, not attributable to causes other than vaccination

- SAE or other potentially life-threatening (Grade 4) event that is determined to be related to study vaccine
- Chronic (>14 days) or recurrent use of systemic corticosteroids and administration of antineoplastic and immunomodulating agents or radiotherapy
- Withdrawal of consent/assent to receive further study vaccination (second vaccination of the 2-dose regimen)
- Participant receives any experimental medication (including experimental vaccines other than the study vaccine) or receives an anti-COVID-19 vaccine or treatment
- Participant previously experienced TTS or heparin-induced thrombocytopenia (HIT), GBS or MIS-C.
- Per the implementation of Amendment 1, the participant has a history of CLS.

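### Section 2.3.1 excludes breastfeeding participants, but exclusion criterion 13 names pregnancy only and no other Section 5 criterion covers breastfeeding

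*Protocol*

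**What the plan says.** The Pregnancy and Birth Control paragraphs of Protocol Section 2.3.1 begin: "The effect of the study vaccine on a fetus or on a nursing baby is unknown". They go on to require contraception and then state: "Participants who are pregnant or breastfeeding will be excluded from the study". For later doses they add one rule: a participant who becomes pregnant gets no more study vaccine but stays in follow-up.

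Section 5 sets the enrolment criteria, to be checked at screening and again before vaccination on Day 1. Criterion 13 in Section 5.2 is "Participant is pregnant". Inclusion criteria 6 and 7 in Section 5.1 deal with contraception and urine pregnancy tests. Section 7.1, the list of reasons to withhold further doses, includes "The participant becomes pregnant". Footnote k of the Schedule of Activities, which governs the pre-vaccination check, covers acute illness and temperature and then adds: "The investigator should also check if any other reasons, as listed in Section 7.1, have been met and would prevent further study vaccination".

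**The concern.** The risk section states a safety exclusion without conditions, and the eligibility list contains only half of it. Sites screen from the numbered criteria. A breastfeeding adolescent who is healthy, uses effective contraception and has a negative urine test meets every inclusion criterion and no exclusion criterion, because a pregnancy test does not detect breastfeeding.

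The person at risk would be an infant who is not a participant. Section 2.2 offers some reassurance. Platform data indicate that the Ad26 vector does not replicate or persist in tissue, and in the rabbit study of the Ebola vaccine on the same vector, pups followed to Lactation Day 28 showed no adverse effect. But no biodistribution study was done with Ad26.COV2.S itself, and the rabbit doses were given before mating and on gestation day 6, not during lactation. The protocol's own position on a nursing baby remains that the effect is unknown.

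There is also a small reporting consequence. SAP Section 6.5 has a major-deviation category for participants who entered without satisfying the criteria. Someone who met the criteria as listed might not be flagged under it.

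**Working it through.** **Text check.** The plan has no figure of its own to reproduce, so the check is a comparison of sections. Breastfeeding, nursing or lactation of a participant is absent from:

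- the inclusion criteria (5.1), exclusion criteria (5.2) and lifestyle considerations (5.3);
- the temporary-delay rules (5.5), which cover acute illness and fever only;
- both Schedule of Activities tables and their footnotes;
- Section 7.1, pregnancy testing (8.2.3), pregnancy reporting (8.3.5) and contraceptive guidance (10.6);
- the SAP.

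Exclusion criterion 5, the closest general criterion, is limited to past or current illness. The only other mention of human breastfeeding is in Section 10.4.4, which makes vaccine exposure through breastfeeding a special reporting situation. That applies after exposure and does not bar entry.

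**Other exclusions stated in Section 2.3.1.** Four conditions can be compared:

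| Stated in 2.3.1 | In Section 5.2? | Does 2.3.1 set a rule for later doses? | In Section 7.1? |
|---|---|---|---|
| Vaccine allergy | Yes, criterion 3 | No | Only anaphylaxis after vaccination |
| Capillary leak syndrome (CLS) | Yes, criterion 24.1 | Yes, second dose | Yes |
| Pregnancy | Yes, criterion 13 | Yes, no further doses | Yes |
| Breastfeeding | **No** | No | No |

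The first three reach Section 5.2 and breastfeeding alone does not. That is the inconsistency. Section 7.1 contains both conditions for which Section 2.3.1 sets a later-dose rule, so nothing promised there is missing.

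**Size.** Inputs: 300 participants, about 70% aged 12 to 15 and 30% aged 16 to 17, with neither sex above 70% in either age group (Protocol Section 4.1). Females are therefore 30% to 70% of each age group.

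- Aged 12 to 15: 0.70 × 300 = 210, so 63 to 147 females.
- Aged 16 to 17: 0.30 × 300 = 90, so 27 to 63 females.
- Total: 90 to 210 females.

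The breastfeeding rate is an assumption, because the documents give none. Expected number = females × rate:

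| Assumed rate | 90 females | 210 females |
|---|---|---|
| 0% | 0 | 0 |
| 0.1% | 0.09 | 0.21 |
| 0.5% | 0.45 | 1.05 |
| 1% | 0.9 | 2.1 |

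**Exposure.** Everyone receives an active dose on Day 1. The second active dose is planned for Day 57 in Groups 4-6 and Day 184 in Groups 1-3, whose Day 57 injection is placebo. A participant breastfeeding at entry need not still be doing so by Day 184.

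**The case against.** **Section 2.3.1 already binds the site.** This stands. Section 10.3.1 makes the investigator responsible for following the whole protocol, and Section 5 requires questions about the criteria to go to the sponsor. A reader might infer that the protocol permits breastfeeding adolescents to enrol. It does not. But a site sees the conflict only if it compares Section 2.3.1 with Section 5.2, so the point is limited to a site working from Section 5 alone.

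**Other procedures may catch it.** Medical history, the physical examination and the contraceptive assessment at screening could bring a recent birth to light, and Section 10.4.4 makes exposure through breastfeeding reportable. These lower the chance of a missed case. None of them is an exclusion.

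**Section 7.1 has the same gap.** A reader might infer this from CLS. Section 2.3.1 says "Individuals with a history of CLS will be excluded from participating in this study (Section 5.2; Exclusion Criterion 24"), Section 5.2 has "History of CLS", and Section 7.1 has "Per the implementation of Amendment 1, the participant has a history of CLS". The documents do not support the parallel. Section 2.3.1 expressly makes CLS a contraindication to a second dose and cites Section 7.1. For breastfeeding it states an entry exclusion only, and its later-dose rule concerns participants who become pregnant, which Section 7.1 contains. Anyone who begins breastfeeding during the study would ordinarily have been pregnant first, and pregnancy already stops vaccination.

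**It is too late to matter.** This largely stands for this trial. Recruitment began on 29 September 2021. The SAP, whose version 5.0 is dated 06 September 2023, already refers to primary analysis results (SAP Section 2), and that analysis uses data up to 28 days after dose 2. Enrolment had probably closed by then. The mismatch remains in the text, and the criteria may be reused in the future pediatric studies that this trial is meant to inform.

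**Conclusion.** The inconsistency between Section 2.3.1 and criterion 13 is real and certain on the text. It reads as a drafting oversight: the other exclusions stated in Section 2.3.1 reach Section 5.2, and nothing in the amendment history describes a decision to admit breastfeeding participants.

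Its practical size is small. Under the assumed range of 0% to 1%, between 0 and 2.1 participants would be expected to be affected, and zero is quite possible. The assumption may be generous, since about 70% of participants are aged 12 to 15. No sample size, estimate or error rate changes. This is a low-severity correction to one eligibility criterion.

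**What to change.** - Change criterion 13 to *Participant is pregnant or breastfeeding*, and confirm it by one question at screening and on Day 1, when the urine pregnancy test is already done.
- If the sponsor means to allow breastfeeding participants, correct the sentence in Section 2.3.1 instead and give the reason.
- Optionally, add breastfeeding to Section 7.1 to protect anyone already enrolled while breastfeeding. Footnote k would then bring it into the check before later doses. This would be a new precaution; it does not correct a stated rule.

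The cost is two added words and one question to at most 210 participants, with no new test, visit or blood draw and negligible effect on recruitment. A change to the criteria needs a formal amendment with ethics committee approval (Section 10.3.1), so it should go into any next amendment or the follow-on pediatric protocols and does not warrant an amendment of its own.

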2.3.2 Benefits of Study Participation

Participants may benefit from clinical testing and physical examination.

The clinical benefits of Ad26.COV2.S in pediatric population have yet to be established. Currently, there is only limited availability of authorized vaccines for the prevention of COVID-19 in the pediatric population. No efficacy can be concluded yet from current data on Ad26.COV2.S. The overall benefit and risk balance for individual participants thus cannot be ascertained. Participants must be informed that this vaccine has not yet been proven to be effective, and it should be assumed that it is not the case until clinical studies are conducted to demonstrate its effectiveness.

2.3.3 Benefit-Risk Assessment of Study Participation

Based on the available data and proposed safety measures, the overall benefit-risk assessment for this clinical study is considered acceptable for the following reasons:

- Only participants who meet all inclusion criteria and none of the exclusion criteria (specified in Section [5](#)) will be allowed to participate in this study. The selection criteria include adequate provisions to minimize the risk and protect the well-being of participants in the study.
- Safety will be closely monitored throughout the study:

In general, safety evaluations will be performed at scheduled visits during the study, as indicated in the Schedule of Activities (Section [1.3](#)).

After each vaccination, participants will remain under observation at the study site for at least 30 minutes (or longer if required by institutional/local practice) and will be closely observed by study site staff. Necessary emergency equipment and medications must be available in the clinic to treat severe allergic reactions. Participants will use a reactogenicity diary in the eCOA to document solicited signs and symptoms. Details are provided in Section 8.3.

The investigator or the designee will document unsolicited AEs, SAEs and MAAEs as indicated in Section 8.3 and Section 10.4.

From the time of local approval of protocol Amendment 1 onwards, TTS is considered to be an AESI (Section 8.3.6.1). Suspected AESIs (thrombotic events and thrombocytopenia [defined as platelet count below 150,000/ μ L] [BC 2021]) must be reported to the sponsor within 24 hours of awareness. Suspected AESIs will be followed up as described in the Schedule of Activities in Section 1.3.4.1.

From the time of local approval of protocol Amendment 1 onwards, MIS-C is considered to be an AESI (Section 8.3.6.2). Suspected AESIs must be reported to the sponsor within 24 hours of awareness. Suspected AESIs will be followed up as described in the Schedule of Activities in Section 1.3.4.2.

Any clinically significant abnormalities (including those persisting at the end of the study/early withdrawal) will be followed by the investigator until resolution or until clinically stable.

An IDMC will be established to monitor safety data on an ongoing basis to ensure the continuing safety of the participants enrolled in this study. This committee will review unblinded data. The IDMC will also review Day 29 and Day 85 safety data at specific occasions during the sequential enrollment of adolescents, as described in Section 4.1. Additional ad hoc reviews may be performed further to the occurrence of any SAE leading to a study pausing situation as outlined in Section 6.8, or at request of the sponsor's medical monitor or designee. The IDMC responsibilities, authorities, and procedures will be documented in the IDMC Charter.

- Several safety measures are included in this protocol to minimize the potential risk to participants, including the following:

Eligibility will be reassessed pre-vaccination at the day of the first vaccination.

The study will start enrollment of the different age groups (16 to 17 years of age and 12 to 15 years of age) simultaneously. Enrollment will begin with the recruitment of participants to a Dose Selection Cohort in both the 1- and 2-dose regimen. Both the 1- and 2-dose regimen will start simultaneously. If it is deemed more appropriate to continue with a lower dose level than either 2.5×10^{10} vp or a 1.25×10^{10} vp dose level, then the use of these doses may be considered and removed in a future protocol amendment.

Adolescents will be monitored in this study to rapidly diagnose COVID-19 and refer for treatment, if applicable. This will mitigate the theoretical potential risk for VAERD when immunized individuals are infected with the virus. The observed induction of neutralizing antibodies and Th1-skewed response by this vaccine in Study COV1001 indicate that the theoretical risk for predisposition of VAERD is minimal.

There are prespecified rules for all participants, that if met would result in pausing of further vaccinations (see Section 6.8), preventing exposure of new participants to study vaccine until the IDMC reviews all safety data (see Section 10.3.6).

Study vaccinations will be discontinued in participants for the reasons included in Section 7.

Contraindications to vaccination are included in Section 5.5.

